5.4.2.3 Time to Alleviation of Symptoms Maintained for a Duration of 43 Hours

Time to alleviation of symptoms is defined as the time from randomization to the point at which a score of 0 or 1 for all Items 1-12 of the COVID-19 Symptom Diary is met and maintained for at least 43 hours.

For new symptoms (i.e., symptoms that develop due COVID-19 which present prior to or post baseline) and pre-existing symptoms (i.e., symptoms that existed prior to developing COVID-19) regardless of whether judged to be worse at screening:

- Alleviation of COVID-19 symptoms (i.e., a score of 0 [none] or 1 [mild] on the COVID-19 Symptom Diary):
 - Severe to mild, or none
 - Moderate to mild, or none
 - Mild to mild or none
 - None to mild or none

The same statistical methods as for the primary endpoint will be used as described in Section [5.3.2](#).

5.4.2.4 Proportion of Patients Requiring Hospitalization for COVID-19

Hospitalizations for COVID-19 are defined as SAEs for which the investigator has cited that the suspected cause was the disease under study and where there is a non-missing hospital admission date. The statistical method is detailed in Section [5.1](#).

5.4.2.5 Time to Return to Afebrile State Maintained for at least 21.5 Hours (Duration of Fever)

Time to return to afebrile state (temperature $\leq 37.5^{\circ}\text{C}$) is defined as the time from randomization to the time of afebrile state maintained for at least 21.5 hours in patients with a fever at baseline. The same statistical methods as for the primary endpoint will be used as described in Section [5.3.2](#).

Where a baseline temperature assessment is missing, the patient will be excluded from the analysis.

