4.5.6.3 Additional COVID-19 Related Assessments

Self-Reported Temperature

Patients will measure temperature four times a day between Days 1 and 5, BID between Days 6 and 10, and once daily between Days 11 and 29 (see [Appendix 3](#)).

COVID-19 Related Medically-Attended Visit(s) Assessment

A COVID-19-related medically-attended visit will be defined as follows: hospitalization, emergency room (ER) visit, urgent care visit, physician's office visit, or telemedicine visit, with the primary reason for the visit being COVID-19.

Only medically-attended visits related to COVID-19, as determined by the investigator, will be recorded in the eCRF. Details will include at minimum:

- Type of visit (hospitalization, ER, urgent care, physician's office visit, telemedicine)
- Date of visit
- Primary reason for COVID-19 related medically-attended visit
- Treatments given for COVID-19 (including, but not limited to, concomitant medications and supplemental oxygen)
- If hospitalization due to COVID-19 was required, include length of visit, whether ICU care was given, or whether mechanical ventilation was required

Any adverse events or concomitant therapies reported to the investigator should be recorded on the respective Adverse Events eCRF or Concomitant Medications eCRF.

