5.3.5.9 Lack of Efficacy or Worsening of COVID-19

Medical occurrences or symptoms of deterioration that are anticipated as part of COVID-19, such as fluctuations in symptoms, should not be recorded as adverse events. However, deterioration that is judged by the investigator to have unexpectedly worsened in severity or frequency or changed in nature at any time during the study should be recorded as an adverse event. When recording an unanticipated worsening

of COVID-19 on the Adverse Event eCRF, it is important to convey the concept that the condition has changed by including applicable descriptors (e.g., accelerated worsening of COVID-19). Any COVID-19-related medically attended visits (defined as hospitalization, ER visit, urgent care visit, physician's office visit, or telemedicine visit, with the primary reason for the visit being COVID-19) should be reported in the eCRF (see Section 4.5.6.3).

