5.3.5.10 Hospitalization or Prolonged Hospitalization

Any adverse event that results in hospitalization (i.e., inpatient admission to a hospital) or prolonged hospitalization should be documented and reported as a serious adverse event (per the definition of serious adverse event in Section 5.2.2), except as outlined below.

An event that leads to hospitalization under the following circumstances should not be reported as an adverse event or a serious adverse event:

- Hospitalization for a preexisting condition, provided that all of the following criteria are met:
 - The hospitalization was planned prior to the study or was scheduled during the study when elective surgery became necessary because of the expected normal progression of the disease
 - The patient has not experienced an adverse event
- Hospitalization based on local COVID-19 isolation policies, such as those in Japan: patients in these countries may be hospitalized for the sole purpose of isolation and not for severe symptoms or inpatient treatment. If deterioration that is judged by the investigator to have unexpectedly worsened in severity or frequency or changed in nature at any time during isolation, it should be recorded as an adverse event.

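### COVID-19 hospitalization is counted only through serious adverse events, so some admissions recorded on the medically attended visit eCRF may not count in this supportive endpoint

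*SAP*

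**What the plan says.** SAP 5.4.2.4 defines the event: "Hospitalizations for COVID-19 are defined as SAEs for which the investigator has cited that the suspected cause was the disease under study". It adds a further condition, that the date of admission is on record. An admission must therefore be an SAE, be attributed to the disease, and carry a date. SAP Table 2 adds that a patient who dies is counted as having the event.

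Three protocol sections decide what reaches the SAE form and what is recorded elsewhere.

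- Section 5.3.5.9: "Medical occurrences or symptoms of deterioration that are anticipated as part of COVID-19, such as fluctuations in symptoms, should not be recorded as adverse events". The exception is "deterioration that is judged by the investigator to have unexpectedly worsened in severity or frequency or changed in nature at any time", which is to be recorded. The section also asks sites to report COVID-19 medically attended visits, hospitalization among them, in the eCRF under 4.5.6.3.
- Section 5.3.5.10: "Any adverse event that results in hospitalization (i.e., inpatient admission to a hospital) or prolonged hospitalization should be documented and reported" as an SAE. The listed exceptions are planned or elective admission for a preexisting condition and stays for isolation only.
- Section 4.5.6.3: "Only medically-attended visits related to COVID-19, as determined by the investigator, will be recorded in the eCRF". The form takes visit type, date and primary reason, and "If hospitalization due to COVID-19 was required, include length of visit, whether ICU care was given, or whether mechanical ventilation was required".

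Two key secondary endpoints also contain hospitalization. SAP 5.4.1.1 defines it by type of visit and primary reason, with no SAE condition. SAP 5.4.1.3 uses hospitalizations that the investigator reports as COVID-19-related complications.

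**The concern.** The definition relies on the adverse event route, and the protocol filters that route through the investigator's judgment of whether a deterioration was to be expected. In a trial of COVID-19, admission for progression of COVID-19 is where that judgment is least clear. An investigator who regards the deterioration as part of the disease can read 5.3.5.9 as saying that no adverse event exists. In that case 5.3.5.10, which starts from an adverse event, is not triggered.

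Two things are at stake. Admissions are likely to be few, so each one lost costs precision. And the same admission could count as a medically attended visit in SAP 5.4.1.1 yet be absent from SAP 5.4.2.4, leaving the clinical study report to explain two hospitalization counts after unblinding.

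**Working it through.** **Can an admission be on the visit form and not count?** Take a patient admitted for COVID-19 whose deterioration the investigator judges to be anticipated.

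1. Protocol 5.3.5.9: the deterioration is not recorded as an adverse event.
2. Protocol 5.3.5.10: the SAE rule applies to an adverse event that results in admission. With no adverse event, nothing triggers it.
3. Protocol 4.5.6.3: the admission is recorded on the visit eCRF as type hospitalization, with its date and reason.
4. SAP 5.4.1.1: by its definition the patient has a medically attended visit. The section names no data source; that it reads this eCRF is an inference from the matching definition.
5. SAP 5.4.2.4: there is no SAE, so the patient does not count unless he or she dies (Table 2).

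Deaths are treated differently. Protocol 5.3.5.7 requires every death in the reporting period on the adverse event form and says explicitly that this includes death from COVID-19 progression. No matching sentence covers admission for progression.

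**The plan's own figure.** The only sizing is for the primary endpoint (SAP 3). The log-rank event count is (z for alpha + z for power)² / [share active × share placebo × (ln HR)²]. With two-sided alpha 0.025 (z = 2.2414), 90% power (z = 1.2816), 2:1 allocation and HR 1.25:

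(2.2414 + 1.2816)² / [(2/3)(1/3)(0.2231)²] = 12.41 / 0.01106, or 1122 events.

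This matches the SAP. At a 90% event rate, 1122/0.9 = 1246.7, against the stated 1248; 1248/0.9 = 1386.7, against about 1386. None of this depends on the hospitalization definition, and no rate or power is stated for hospitalization.

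**Illustration of size.** From the documents: 1248 evaluable patients at 2:1 (416 placebo, 832 active) and two-sided 0.025. Assumed: placebo rate p of 4, 6 or 8%, active rate p/2, and 20% of admissions missed equally in both arms, so that both rates are multiplied by 0.8.

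With p0 and p1 the recorded rates and d = p0 − p1:

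- S = √[p0(1−p0)/416 + p1(1−p1)/832]
- Unpooled variance: power = Φ(d/S − 2.2414)
- Pooled null variance: power = Φ((d − 2.2414·S₀)/S), where S₀ = √[p̄(1−p̄)(1/416 + 1/832)] and p̄ is the overall rate

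At p = 4% with full capture, d = 0.020, S = 0.01076 and S₀ = 0.00967. Unpooled: Φ(1.858 − 2.241) = 35%. Pooled: Φ((0.020 − 0.02167)/0.01076) = 44%.

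| Placebo rate | Expected admissions, full / 80% | Unpooled power, full / 80% | Pooled power, full / 80% |
|---|---|---|---|
| 4% | 33.3 / 26.6 | 35% / 28% | 44% / 36% |
| 6% | 49.9 / 39.9 | 52% / 42% | 61% / 51% |
| 8% | 66.6 / 53.2 | 67% / 55% | 74% / 64% |

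The absolute power depends on the variance used. The loss does so much less: about 7 to 12 points unpooled and 8 to 10 pooled. The risk difference shrinks in proportion to capture, while the risk ratio is unchanged when capture is equal in the two arms.

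**The case against.** The strongest reply is that COVID-19 admissions are meant to be SAEs. Inpatient hospitalization is a seriousness criterion in Protocol 5.2.2. The exceptions in 5.3.5.10 do not include COVID-19 progression, and a separate exemption for isolation stays would hardly be needed if COVID-19 admissions were generally outside SAE reporting. The only example of anticipated deterioration in 5.3.5.9 is fluctuating symptoms. Patients thought likely to deteriorate soon and need admission are excluded at entry, which makes a later admission harder to call anticipated. The SAE route also screens out isolation-only stays, which the visit form does not exclude in terms.

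Much of this stands. A reader might infer that the protocol diverts COVID-19 admissions away from the adverse event form, so that the endpoint systematically under-counts them. The text does not say so. It asks for visits to be recorded in the eCRF, not recorded there instead of as adverse events, and 4.5.6.3 separately sends adverse events to their own form. The two routes run in parallel, and many sites would probably use both.

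The importance is also limited. The endpoint is supportive and outside multiplicity control (SAP 2.2 and 5.1), so power at 0.025 has no confirmatory meaning here. An admission missing from 5.4.2.4 may still appear in 5.4.1.1 or 5.4.1.3.

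What the reply does not remove is that the SAE rule starts from an adverse event, that progression is named explicitly for deaths but not for admissions, and that the SAP plans no check of one source against the other.

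**Conclusion.** The point holds as a gap in the endpoint definition that can lose admissions. It does not show that admissions will be lost. The documents give no basis for the share missed, and it could be close to zero if sites file SAEs as 5.3.5.10 suggests. On the assumptions shown, the cost would be about 7 to 12 points of power for a supportive comparison and a fifth of the admissions.

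A reader might also infer a bias in favor of one arm. Nothing in the documents supports that: the study is double-blind, so missed admissions would be expected to be similar in the two arms, and the expected harm is fewer events and inconsistent counts. The primary analysis and the type I error control are unaffected. The change is worth making because it is cheap and uses data already collected.

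**What to change.** Reword SAP 5.4.2.4 so that a COVID-19 hospitalization is either an admission recorded on the medically attended visit eCRF as type hospitalization with COVID-19 as the primary reason, or an SAE admission attributed to COVID-19. Exclude stays for isolation only, in line with Protocol 3.1 and 5.3.5.10. Keep the Table 2 rule for death.

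Before unblinding, produce one listing that sets the two sources side by side for each patient, and resolve admissions that appear in only one of them or lack a date. Align the hospitalization component across SAP 5.4.1.1, 5.4.1.3 and 5.4.2.4, or state why the definitions differ.

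The cost is SAP wording, one reconciliation listing, and a manual check for isolation-only stays, which the SAE route now screens out. No new data are needed. If sites do file SAEs consistently, the listing will show few discrepancies and the endpoint will hardly change.

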5.4.2.6 Proportion of Patients with Any Post-Treatment Infection

Post-treatment infections are defined as any treatment-emergent adverse event with a primary system organ class of infections and infestations. The statistical method is detailed in Section 5.1.

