4.3.2.1 RO7496998 (AT-527) and Placebo

RO7496998 (AT-527) is provided as 275 mg tablets; two tablets will be administered orally BID from Day 1 to Day 5. Matching placebo is provided as 275 mg tablets; two tablets will be administered orally BID from Day 1 to Day 5.

RO7496998 (AT-527) (or matching placebo) should be taken orally at 12-hour intervals (± 2 hours). If the first study dose is taken prior to 2:00 p.m. on Day 1, the next dose should be taken in the evening of the same day (i.e., prior to midnight on the same calendar day with a minimum of 10 hours between doses). For these patients, the final (tenth) dose will be taken in the evening of Day 5. However, if the first study dose is taken after 2:00 p.m. on Day 1, the next dose should be taken in the morning of Day 2. For these patients, the final (tenth) dose will be taken on the morning of Day 6.

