6.5 SAFETY ANALYSES

All safety analyses will be based on the safety analysis population, which will consist of all randomized patients who received at least one dose of study drug, with patients grouped according to treatment received. Safety analyses will include adult and adolescent patients. Additional safety analyses divided by age subgroup may also be produced and will be specified in the SAP.

Safety will be assessed through descriptive summaries of treatment emergent adverse events (nature, frequency, severity, and causality). Adverse events will be listed. All verbatim adverse event terms will be mapped to MedDRA thesaurus terms, and adverse event severity will be graded according to the NCI CTCAE v5.0 scale. Safety will be assessed through descriptive summaries of adverse events, vital sign measurements (including SpO₂), and laboratory test results (serum chemistry and hematology including complete blood count with differential and platelet counts).

A treatment-emergent adverse event is defined as any new adverse event reported or any worsening of an existing condition on or after the first dose of study drug.

Separate summaries will be generated for serious adverse events, deaths, adverse events leading to discontinuation of study drug, and adverse events of special interest.

Adverse events will be summarized by MedDRA term, appropriate thesaurus level, and toxicity grade.

Descriptive summaries of laboratory values at baseline and throughout the study will be tabulated by treatment arm. For selected parameters, changes from baseline and the proportion of patients experiencing clinically significant changes relative to baseline will be summarized by treatment arm.

Values, along with change from baseline, will be summarized using descriptive statistics for each vital sign parameter.

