Key Secondary: Proportion of patients with ≥ 1 COVID-19 related medically attended visit	Patients with ≥ 1 COVID-19 related medically attended visit through to study end (including early termination visits)	Treatment-policy strategy approach will be taken. Patients are followed, assessed and analyzed irrespective of their completion of the planned course of the study treatment and irrespective of rescue and concomitant therapy (contd.)	Composite strategy where patient considered as having the event if they die (contd.)	Difference in proportion of patients between treatments (contd.)	The outcome measure up to point of study withdrawal will be used (contd.)
Secondary: Proportion of patients with any post treatment infection	Patients with any post treatment infection through to study end (including early termination visits)		Not an intercurrent event as it is the outcome measure		
Key Secondary: Frequency (Proportion) of COVID-19 related complications (including hospitalizations and deaths)	Patients with a medically confirmed COVID-19 related complication through to study end (including early termination visits)				
Key Secondary: Proportion of patients with all-cause mortality	Patients with all-cause mortality through to study end (including early termination visits)				

Table 2 Estimands (cont.)

Endpoint	Variable or Outcome Measurement	Intercurrent Events		Population-Level Summary for the Variable	Handling of Missing Data
		Treatment Withdrawal/Rescue/Concomitant Medications	Death		
Secondary (Virology): Change from baseline in amount of SARS-CoV-2 virus RNA	Amount of SARS-CoV-2 virus RNA, as measured by RT-qPCR at Day 3, Day 5, Day 7 and Day 14	Treatment-policy strategy approach will be taken. Patients are followed, assessed and analyzed irrespective of their completion of the planned course of the study treatment and irrespective of rescue and concomitant therapy.	While on treatment approach where the outcome measure up to point of intercurrent event will be used	Difference in mean change from baseline between treatments	The outcome measure up to point of study withdrawal will be used
Secondary (Virology): AUC in amount of SARS-CoV-2 virus RNA	Amount of SARS-CoV-2 virus RNA, as measured by RT-qPCR to Day 14			AUC for each treatment	

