1.2 STUDY DESIGN

This is a Phase III, placebo-controlled, double-blind, multicenter study to assess the efficacy, safety, antiviral activity, and pharmacokinetics of RO7496998 (AT-527) compared with placebo in non-hospitalized adult and adolescent patients with mild to moderate coronavirus disease 2019 (COVID-19) in the outpatient setting.

[figure not shown]
The study will enroll approximately 1386 patients (including approximately 100 adolescents, up to a maximum of 150, with the remaining patients being adults) with confirmed severe acute respiratory syndrome coronavirus (SARS-CoV-2) infection.

The study consists of two periods: a 5-day treatment period and a 28-day safety and efficacy follow-up period, with mandatory study visits on Days 1, 2, 3, 5, 7, and 14. Some of these visits may be conducted by mobile nursing or telemedicine. In addition to mandatory study visits, there will be telephone calls on Day 21 (± 2 days) and Day 28 (± 2 days). The end of study visit will take place on Day 33 (± 3 days), preferentially as a telephone consult but may be conducted in-person in some instances, such as if the patient is enrolling in a longer-term follow-up RO7496998 (AT-527) study. The total study duration for each patient will be approximately 33 days.

The primary analysis will be performed once the data from the last patient's last visit has been collected in the database and all data has been cleaned and verified.

The study schema is shown in [Figure 1](#).

Figure 1 Study Schema

Randomization to 2:1 ratio (active:placebo).

BID=twice a day; N=number of patients; R=randomization; SARS-CoV=severe acute respiratory syndrome coronavirus; TC=telephone call.

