Secondary safety endpoints and other AE analyses will be assessed through descriptive summaries of treatment-emergent adverse events unless otherwise stated. A treatment-emergent adverse event is defined as any new adverse event reported or any worsening of an existing condition on or after the first dose of study treatment. Data reported will include data from baseline up until the patient completes/discontinues from the study and including data from the early termination visit, if applicable. All verbatim adverse event terms will be mapped to Medical Dictionary for Regulatory Activities (MedDRA) Preferred Terms, and adverse event severity will be graded according to the NCI CTCAE v5.0 scale. Adverse events will be tabulated by system organ class (in decreasing order of overall incidence) and by MedDRA Preferred Term (in decreasing order of overall incidence), unless otherwise stated.

Data will be analyzed per the reported assessment; time windows will not be implemented unless otherwise specified.

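### The post-treatment infection endpoint counts from the first dose and does not exclude COVID-19, so recorded COVID-19 worsening can be counted together with other infections

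*SAP*

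**What the plan says.** The protocol lists the proportion of patients with any post-treatment infection as a secondary efficacy endpoint (Sections 2 and 6.4.2) but does not define it. The definition is in SAP 5.4.2.6: "Post-treatment infections are defined as any treatment-emergent adverse event with a primary system organ class of infections and infestations".

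SAP 5.1 defines a treatment-emergent event as "any new adverse event reported or any worsening of an existing condition on or after the first dose of study treatment". Protocol 6.5 matches it: "any new adverse event reported or any worsening of an existing condition on or after the first dose of study drug". SAP Table 2 counts this endpoint through to study end.

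Both documents separate treatment from follow-up; SAP 1.2 describes "a 5-day treatment period and a 28-day safety and efficacy follow-up period". Protocol 4.3.2.1 adds, for patients whose first dose falls after 2 p.m.: "For these patients, the final (tenth) dose will be taken on the morning of Day 6".

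Protocol 5.3.5.9 governs how the study disease is recorded. The anticipated course, including symptom fluctuation, stays off the adverse event form. What goes on it is "deterioration that is judged by the investigator to have unexpectedly worsened in severity or frequency or changed in nature at any time during the study", and the example descriptor is "accelerated worsening of COVID-19". Protocol 5.3.5.7 also puts a death due solely to the disease on that form, under a COVID-19 progression term.

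Under SAP 5.1 the endpoint is analysed in the efficacy-evaluable set with a stratified Cochran-Mantel-Haenszel test. The output is a difference in proportions, an odds ratio, 97.5% confidence intervals and a p-value.

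**The concern.** The label and the derivation differ in two ways. First, the name points to infections arising after treatment, but the count begins with the first dose. Second, every patient in the efficacy-evaluable set has a centrally confirmed SARS-CoV-2 infection, worsening of an existing condition counts as treatment-emergent, and no rule removes COVID-19 terms from the infections class.

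The second is the more important. The drug is meant to reduce COVID-19 worsening. If recorded worsening enters the count, a between-arm difference may partly re-measure efficacy on the study disease, yet be read as an effect on other infections. If the added events are unrelated to treatment, they dilute a real difference in other infections. The endpoint has a formal test and sits among the efficacy results, so readers will interpret it.

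**Working it through.** The documents state no rate, effect size or power for this endpoint, so there is no figure to reproduce. The check is a trace of the definition, followed by illustrations on assumed rates.

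**Step 1: the window.** SAP 5.4.2.6 points to treatment-emergent, SAP 5.1 starts that at the first dose, and Table 2 ends the count at study end. Dosing covers Days 1 to 5, or runs to the morning of Day 6, of about 33 days:

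- 5/33 = 15.2%
- 6/33 = 18.2%

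All of that time counts as post-treatment. This step needs no assumption.

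**Step 2: the study disease.**

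| Element | Source | Consequence |
|---|---|---|
| Anticipated COVID-19 course | Protocol 5.3.5.9 | Not an adverse event, so not counted |
| Unexpected worsening | Protocol 5.3.5.9 | Adverse event; counted if coded to the infections class |
| Death solely from COVID-19 | Protocol 5.3.5.7 | On the adverse event form; counted if so coded |
| Exclusion of COVID-19 terms | None found | No filter |

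The documents say that terms are mapped to MedDRA, not which class a given COVID-19 term falls in. Protocol 1.1 calls COVID-19 an infectious disease, so the infections class is a reasonable inference, but it remains one.

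**Step 3: whether anything else repairs it.** SAP Appendix 1 does not mention the endpoint. The adjudication in SAP 1.2.2 serves only the complications endpoint. The onset bands in SAP 5.6.2 (Days 1-7, 8-14, 15 or later) apply to adverse event tables, and the first band mixes dosing and post-dosing days.

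**Step 4: illustrations.** All rates are assumptions. With 1248 patients at 2:1, the arms are 832 active and 416 placebo. For other infections at rate *q* and recorded worsening at rate *w*, taken as independent, the endpoint rate is *p* = 1 − (1 − *q*)(1 − *w*). The chance of nominal significance uses an unstratified normal approximation at two-sided 0.025: Φ[(|*p*₁ − *p*₂| − 2.241·SE₀)/SE₁], with SE₀ pooled and SE₁ unpooled.

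(a) No true difference in other infections (*q* = 3% in both arms), fewer worsening events on active. For 2% against 5%: 1 − 0.97×0.98 = 4.94% and 1 − 0.97×0.95 = 7.85%.

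| Worsening, active / placebo | Endpoint, active / placebo | Chance of nominal significance |
|---|---|---|
| 1% / 2% | 3.97% / 4.94% | 8% |
| 2% / 4% | 4.94% / 6.88% | 21% |
| 1% / 3% | 3.97% / 5.91% | 25% |
| 2% / 5% | 4.94% / 7.85% | 43% |

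The nominal level is 2.5%.

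(b) A true difference in other infections, with treatment-independent events added equally to both arms.

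| Added to both arms | 2% vs 4%: odds ratio, power | 3% vs 6%: odds ratio, power |
|---|---|---|
| 0% | 0.49, 44% | 0.48, 61% |
| 1% | 0.59, 33% | 0.55, 51% |
| 2% | 0.66, 26% | 0.61, 44% |
| 3% | 0.70, 21% | 0.65, 38% |
| 5% | 0.77, 16% | 0.71, 29% |

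(c) Opposing effects: other infections 4% active and 2% placebo, worsening 2% active and 4% placebo. Both arms give 1 − 0.96×0.98 = 5.92%, so the endpoint shows no difference.

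The direction of the distortion therefore depends on the assumptions.

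**The case against.** The strongest reply is that this is mostly a naming matter on a low-stakes endpoint. Several parts of that stand.

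- **Stakes.** The endpoint is listed under SAP 5.4.2 as supportive, outside the key secondaries in 5.4.1. No alpha, sample size or confirmatory claim depends on it.
- **Narrow route.** A reader might infer that, because every patient enters with COVID-19, the study disease floods the count. The documents do not support that. An event must be new or worsened from the first dose, and Protocol 5.3.5.9 keeps the anticipated course off the form.
- **Other tables.** A reader might infer that an excess of other infections would be invisible. It would not be. SAP 5.1 tabulates adverse events by system organ class and Preferred Term, and SAP 5.6.2 adds onset bands and listings. Those tables are descriptive and use the safety-evaluable set, so they show the components without correcting the tested endpoint.
- **No stated question.** A reader might say the endpoint fails to answer its own question. The protocol states none beyond the name, and post-treatment could mean after treatment start. Neither document settles this, although both use separate treatment and follow-up periods.
- **Starting at the last dose.** That would match the label, but it gives unequal risk windows to early discontinuers, ties the start to something treatment can affect, and fits poorly with the treatment-policy strategy in Table 2.

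What the reply does not remove is the missing rule for COVID-19 terms in an endpoint that is formally tested.

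**Conclusion.** The point holds in a limited form. That dosing-period events count as post-treatment follows directly from the text and affects 15% to 18% of the study window. That recorded COVID-19 worsening can be counted follows from the recording rules and the absence of an exclusion, on condition that those terms code to the infections class. Where they do, the endpoint cannot separate other infections from COVID-19 worsening.

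The size cannot be derived from the documents. The figures in the working are illustrations on assumed rates and should not be cited as expected effects. The consequence is for interpretation of one supportive endpoint, not for the trial's conclusions. It is worth correcting because the change is small and can be made before unblinding.

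**What to change.** Amend SAP 5.4.2.6 and the matching row of Table 2 before unblinding:

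1. Exclude COVID-19 and SARS-CoV-2 terms, including progression, using a term list fixed in advance by blinded review.
2. Keep the current all-terms derivation as a supporting table, so nothing already planned is lost.
3. Rename the endpoint as treatment-emergent infection (excluding COVID-19), so the label matches the first-dose window, and record the change in SAP Appendix 1.
4. If wanted, show events with onset after the last dose as a supporting split rather than as the main count.

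The cost is a few lines of SAP text, a short blinded review of coded terms and slightly fewer counted events. No new data are needed, and no sample size, power or alpha figure changes.
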